### 11.1 Adverse Events

An adverse event (AE) is any untoward medical occurrence in a subject receiving study drug and which does not necessarily have a causal relationship with this treatment. For this protocol, the definition of AE also includes worsening of any pre-existing medical condition. An AE can therefore be any unfavorable and unintended or worsening sign (including an abnormal laboratory finding), symptom, or disease temporally associated with the use of Sym004, whether or not related to use of the Sym004. Abnormal laboratory findings without clinical significance (based on the PI's judgment) should not be recorded as AEs. But laboratory value changes that require therapy or adjustment in prior therapy are considered adverse events.

From the time the subject signs the informed consent form through the End of Study visit (as defined in Section 10.5), all AEs must be recorded in the subject medical record and adverse events case report form.

AEs will be assessed according to the CTCAE version 4.0. If CTCAE grading does not exist for an AE, the severity of the AE will be graded as mild (1), moderate (2), severe (3), life-threatening (4), or fatal (5).

Attribution of AEs will be indicated as follows:

- Definite: The AE is clearly related to the study drug
- Probably: The AE is likely related to the study drug
- Possible: The AE may be related to the study drug
- Unlikely: The AE is doubtfully related to the study drug
- Unrelated: The AE is clearly NOT related to the study drug

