#### 7.1.1 Dose Modification

For subjects receiving 18 mg/kg, the dose of Sym004 may be reduced by up to two dose levels, if the subject experiences grade 3-4 non-hematologic toxicities secondary to Sym004, e.g. skin toxicities, electrolyte disturbances, and gastrointestinal symptoms, or grade 4 neutropenia or thrombocytopenia. Following the initial dose of 18 mg/kg every 2 weeks, if the subject needs to have their dose of Sym004 reduced due to an aforementioned toxicity, then their next dose will be 15 mg/kg every 2 weeks. If another reduction in dose is necessary, the subsequent dose will be 12 mg/kg every 2 weeks. If dose reduction is required more than two times, the patient will be removed from the study.

#### 7.1.2 Dose Modification Post-Amendment 31

For subjects receiving 24 mg/kg, the dose of Sym004 may be reduced by up to two dose levels, if the subject experiences grade 3-4 non-hematologic toxicities secondary to Sym004, e.g. skin toxicities, electrolyte disturbances, and gastrointestinal symptoms, infusion-related reactions, or grade 4 neutropenia or thrombocytopenia. Exceptions to this dose reduction include grade 3 nausea, vomiting, diarrhea or fatigue lasting  $\leq$  5 days with supportive care or grade 3 asymptomatic electrolyte abnormalities. Following the initial dose of 24 mg/kg every 2 weeks, if the subject needs to have their dose of Sym004 reduced due to an aforementioned toxicity, then their next dose will be 18 mg/kg every 2 weeks. If another reduction in dose is necessary, the subsequent dose will be 15 mg/kg every 2 weeks. If dose reduction is required more than two times, the patient will be removed from the study.

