#### 7.1.3 Safety Considerations

According to the Sym004 Investigator's Brochure (v. 8.0, 13-Mar-2017), skin toxicities have been the most frequently reported AEs. To date (20 Jan 2017), approximately 380 subjects with solid tumors, including

subjects with recurrent/metastatic SCCHN, mCRC, ESCC and NSCLC, have been treated with Sym004 in weekly doses of up to 12 mg/kg and in doses every other week of up to 18 mg/kg in ongoing Symphogen-sponsored studies. Anti-EGFR related skin toxicities (including rash, pruritus, skin fissures, dry skin, erythema, and paronychia) have been observed in more than 90% of subjects in the completed and ongoing clinical trials. In subjects who had previously received anti-EGFR mAb therapy, Grade 3 skin toxicities were frequently reported; 50-69% of subjects at a dose of 9 or 12 mg/kg weekly (Sym004-01 Parts B and C and Sym004-02) and 33.3% and 41.2% of subjects at dose levels of 12 mg/kg and 18 mg/kg, respectively, every other week (Sym004-01 Parts D and E).

Other adverse events (AEs) associated with anti-EGFR mAbs, such as electrolyte disturbances (in particular hypomagnesemia), mucositis, and diarrhea were also frequently observed in the completed and ongoing trials. In clinical trials for which AE data are available (Sym004-01-Parts A, B, C, D, E, Sym004-02, and EMR 200637-001-Part A) hypomagnesemia was reported in 54-77% of subjects, and 0-38% of subjects experienced Grade 3 or 4 hypomagnesemia. In the Sym004-01 and Sym004-02 clinical trials, events of hypomagnesemia also represented the majority of serious adverse events (SAEs) that were considered to be related to Sym004 therapy. Serious clinical complications of hypomagnesemia have not been observed. Mucositis was observed in up to 40% of subjects, but the number of subjects experiencing Grade 3 mucositis was low (1 subject). Diarrhea has been reported in up to 59% of subjects; and ≤ 10% of subjects experienced Grade 3 diarrhea. Infusion related reactions have also been observed.

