### 13.5.1 Key Secondary Objective: Safety

Within each cohort and dose level, the proportion of patients who experience grade 3, 4, or 5 adverse events that are possibly, probably, and definitely related to protocol treatment will be estimated.

In addition, for each type of toxicity, the maximum grade experienced by each patient will be summarized with frequency distributions. Two adverse experience tabulations will be generated, one that includes all toxicities regardless of attribution, and one that includes only toxicities that are possible, probably, and definitely related to Sym004 treatment.

Patients who have their dose escalated from 18 mg/kg to 24 mg/kg will be included in toxicity summaries for 18 mg/kg and 24 mg/kg. The toxicity experienced prior to dose escalation will be summarized with the other patients treated at the 18 mg/kg dose level; whereas, the toxicity experienced after dose escalation will be included in the summary of adverse events associated with 24 mg/kg.

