### 13.7.4 Initial Toxicity Monitoring among Patients Treated with 24 mg/kg Sym004

Given limited experience with 24 mg/kg Sym004, the first 3-6 patients will be slowly accrued and carefully monitored for unacceptable toxicity (see Section 7.1.2).

The first patient, regardless of cohort, will be treated and observed for 1 cycle before the accrual of a second patient. During this period of observation, the patient will receive at minimum 2 full doses of Sym004 and be followed until the end of Cycle 1. If the patient experiences an unacceptable adverse event (refer to Section 7.1.2), the study will be suspended and the patient's experience will be discussed with Symphogen to determine whether patient accrual should continue. Otherwise, 2 additional patients will be treated.

The second and third patient can be accrued at the same time. However, further accrual after the 3rd patient is suspended until completion of 1 cycle of therapy. After the first 3 patients have been observed, the number of patients with unacceptable toxicity will be determined.

- If none of the first 3 patients has an unacceptable toxic event, accrual will continue without further slowed accrual.
- If 2 of the first 3 patients has an unacceptable toxicity, the study will remain suspended. Results will be discussed with Symphogen with the expectation that accrual will be terminated.
- If 1 of the first 3 patients has an unacceptable toxicity, an additional 3 patients can be accrued after which accrual will be suspended until all patients have been observed for at least 1 cycle. If none of the additional 3 patients experiences an unacceptable toxicity, then accrual will resume without the requirement of staggered entry. If 1 of these 3 patients experiences an unacceptable toxicity, the study will remain suspended while a discussion occurs with Symphogen to determine if accrual is terminated.

For initial monitoring of the 24 mg/kg dose of Sym004, an unacceptable adverse event is defined as any grade 3, 4, or 5 adverse event that is definitely, possibly, or potentially related to Sym004 treatment.

Patients who have their dose escalated from 18 mg/kg to 24 mg/kg will be considered as part of this interim analyses of toxicity at the 24 mg/kg if they are among the first 3 (or 6) patients who receive Sym004 at the 24 mg/kg dose level.

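### Untreated grade 3-4 laboratory values can go unrecorded as adverse events, and so miss both the key secondary safety proportion and the 24 mg/kg toxicity check

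*Combined protocol and SAP*

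**What the plan says.** The recording rule is in Section 11.1: "Abnormal laboratory findings without clinical significance (based on the PI's judgment) should not be recorded as AEs". The next sentence limits it: "But laboratory value changes that require therapy or adjustment in prior therapy are considered adverse events". Neither sentence mentions a CTCAE grade, although the same section grades adverse events by CTCAE version 4.0.

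Two safety measures draw on what is recorded:

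- Section 13.5.1 estimates, separately by cohort and dose: "the proportion of patients who experience grade 3, 4, or 5 adverse events that are possibly, probably, and definitely related to protocol treatment". It adds that "for each type of toxicity, the maximum grade experienced by each patient will be summarized with frequency distributions", in two tabulations of adverse experiences (any attribution, and related only). It names no table built from laboratory values.
- Section 13.7.4 governs the first 3-6 patients at 24 mg/kg. It defines an unacceptable event as "any grade 3, 4, or 5 adverse event that is definitely, possibly, or potentially related to Sym004 treatment". It also refers twice to Section 7.1.2, where "grade 3 asymptomatic electrolyte abnormalities" appear among the exceptions to dose reduction.

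The Section 10 schedule has CBC and CMP + Mg drawn every 2 weeks from Cycle 1 Day 15. Section 7.1.3 reports from earlier trials that "0-38% of subjects experienced Grade 3 or 4 hypomagnesemia".

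**The concern.** Electrolyte disturbance is an expected effect of Sym004 (11.1.1), and the blood tests needed to grade it are drawn on a fixed schedule. Yet whether a severe value counts depends first on whether anyone treated it, and then on the judgement of a sponsor-investigator in a trial with no blinding (7.1.6) and no external safety board (11.7). A value not recorded as an adverse event is given no attribution as an event, so it cannot enter a measure restricted to related events.

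Two results could be affected. The key secondary proportion could be too low. The 24 mg/kg check could also be affected, and it decides on so few patients that one missing event turns 1 of 3 into 0 of 3 and ends slowed accrual.

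**Working it through.** The plan states no expected value for the key secondary proportion and no operating characteristics for the 24 mg/kg check, so there is no figure to reproduce. Steps 1, 2 and 5 compare the text. Steps 3 and 4 are illustrations on assumed inputs.

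**Step 1. Path of a grade 3-4 laboratory value.**

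| Situation | Recorded under 11.1? | Reaches 13.5.1 and 13.7.4? |
|---|---|---|
| Needs therapy or adjustment of therapy | Yes | Yes, if judged related |
| Untreated, judged clinically significant | Yes | Yes, if judged related |
| Untreated, judged not significant | No | No |

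Only the third row is a gap.

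**Step 2. What can fall in the third row.** Section 7.1.5 says hypomagnesemia will be treated, and 11.1.1 stresses early magnesium replacement, so most severe hypomagnesemia should fall in the first row. Candidates for the third row are untreated, asymptomatic changes in other electrolytes, liver enzymes or blood counts. The panels in 10.9.6 include ALT and absolute lymphocyte count, for example, and neither has a numeric re-treatment threshold in 10.4.

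**Step 3. Effect on the key secondary proportion.** Let s be the share of patients whose only related grade 3 or higher event is a laboratory value, and u the share of those untreated and judged not significant. The loss is s × u. The documents give neither. With s = 20% assumed:

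| u (assumed) | Loss | Of 36 (Cohort 1) | Of 29 (Cohort 2) |
|---|---|---|---|
| 5% | 1 point | 0.36 patients | 0.29 patients |
| 10% | 2 points | 0.72 | 0.58 |
| 25% | 5 points | 1.8 | 1.45 |
| 50% | 10 points | 3.6 | 2.9 |

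If s is zero, the loss is zero.

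**Step 4. Effect on the 24 mg/kg check.** The rule passes on 0 of 3, or on 1 of 3 followed by 0 of 3. With p the chance that a patient has a recorded unacceptable event and q = 1 − p,

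P(pass) = q³ + 3pq² × q³.

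This takes any pause after an event in patient 1 as resolved by continuing. If such an event instead counts as not passing, P(pass) = q(q² + 2pq × q³). Assume other related severe events in 20% of patients, severe laboratory events in 20%, independence, and a share r of laboratory events recorded: p = 1 − 0.80 × (1 − 0.20r).

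| r | p | P(pass) | P(pass), patient 1 event not passing |
|---|---|---|---|
| 100% | 0.360 | 0.378 | 0.339 |
| 90% | 0.344 | 0.408 | 0.366 |
| 75% | 0.320 | 0.454 | 0.407 |
| 50% | 0.280 | 0.536 | 0.482 |
| 0% | 0.200 | 0.709 | 0.643 |

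For r = 90%: q = 0.656, q³ = 0.2823, and 0.2823 + 3 × 0.344 × 0.4303 × 0.2823 = 0.408. The last row is an outer bound, because treated values must be recorded. With no laboratory toxicity, recording makes no difference (0.709 throughout).

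**Step 5. Sections 13.7.4 and 7.1.2.** By its own definition, 13.7.4 counts any related grade 3-5 event. Its references to 7.1.2 lead to a list that excepts asymptomatic grade 3 electrolyte abnormalities from dose reduction. A reader cannot tell whether such an event, once recorded, counts in the check. This is separate from the recording gap, and changing 11.1 would not resolve it.

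**The case against.** The strongest reply is that the protocol already catches what matters. Treated abnormalities are adverse events, and hypomagnesemia is to be treated. Section 10.4 applies ANC, platelet, AST, bilirubin and creatinine limits before each infusion, and requires attributable grade 3 or higher toxicity to settle to grade 2 or lower. Section 11 has the investigator look for events at every visit, including through study assessments. A value that delays or reduces a dose is hard to call insignificant.

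This stands as far as it narrows the gap. It does not close it. Treatment under 7.1.5 is at the physician's discretion, so the safeguard also rests on judgement. The emphasis on replacement in 11.1.1 is on magnesium, although low calcium and potassium are listed as expected too. Section 10.4 does not require an adverse event entry and sets no numeric limit for electrolytes, ALT or lymphocytes.

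Three stronger readings are tempting and are not supported:

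- **That up to 38% of patients could be lost.** The 0-38% is grade 3-4 hypomagnesemia in earlier trials, treated or not. Here it would mostly be treated and so recorded.
- **That 7.1.2 names asymptomatic grade 3 electrolyte abnormalities as an expected category.** It lists them only as exceptions to dose reduction. The expected reactions are in 11.1.1.
- **That the comparison of doses is biased because judgement shifted.** The electrolyte exception is in 7.1.2 and not in 7.1.1, but both concern dose reduction. One recording rule and one blood-test schedule apply at both doses, the 13.5.1 summaries are descriptive, and nothing shows that judgement changed.

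**Conclusion.** The gap is real and narrow. Untreated grade 3-4 laboratory values judged not clinically significant can be absent from both the key secondary proportion and the 24 mg/kg check, and no planned summary would reveal it.

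The direction is clear: the recorded rate can only be lowered, and the check made easier to pass. The size is not derivable. The losses of 1-2 or 5-10 points, and the pass probabilities, rest on assumed event rates and unrecorded shares; the larger values fit poorly with the protocol's emphasis on treating hypomagnesemia. The loss may be well under one patient per cohort. The case for change is that an objective measure is already being collected and costs little to use. This is a worthwhile improvement, not a flaw that undermines the trial.

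**What to change.** 1. **Section 13.5.1: add a table.** Suggested text: *For each laboratory parameter in the CBC and CMP + Mg that has a CTCAE grade, the worst on-treatment grade will be derived from the measured values and tabulated by cohort and dose level, for patients treated at 18 mg/kg and at 24 mg/kg.* This gives both doses the same measure, free of judged significance. It carries no attribution, so it supplements the key secondary proportion. It assumes that the 18 mg/kg laboratory values are retained; the documents do not list the eCRF fields.

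2. **Section 11.1: add a sentence for the 24 mg/kg patients.** Suggested text: *Any laboratory value of CTCAE grade 3 or higher is recorded as an adverse event with attribution, regardless of judged clinical significance.* Of these two changes, only this one reaches the 13.7.4 check. About 25 patients were treated at 18 mg/kg under the present rule, and that dose is closed to enrolment (13.8.2). Either apply the sentence to them retrospectively, or state that AE-based rates are not like for like across doses. Otherwise the amendment itself would create a difference between doses.

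3. **Reconcile 13.7.4 with 7.1.2**, so that it is clear which events count as unacceptable in the check.

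The cost is some extra adverse event entries, one extra table, and possibly a slightly higher reported severe-event rate.

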## 10.5 End of Treatment

The End of Treatment visit, i.e. the date of a subject's last treatment visit, should include:

- Interval history and full physical exam, including a full neurologic assessment and KPS
- Vital signs, including blood pressure and weight
- Hematology including CBC/differential
- CMP + Mg
- MRI of the brain
- Quality of life measurements (should be performed prior to other study-related evaluations at study visits, if at all possible)
- Skin toxicity assessment
- Toxicity assessment

If a subject goes off study and does not return to clinic as part of a regular study visit, not all tests listed above may be obtained as part of end of treatment, e.g. magnesium. If this occurs, only the assessments that are reasonably obtainable will be collected as part of end of treatment.

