## 10.6 Follow-up Period

Patients will be followed for safety a minimum of 30 days after last dose of study drug, and also followed for any new and/or unresolved serious adverse events considered related to study therapy. Once "off study," subjects will be followed for progression (for patients who came off study prior to disease progression) and survival status (all patients) at least 1 year, if possible. Subjects not returning to Duke will be contacted via phone or information will be obtained through their local physician every 3 months to determine time of progression or survival.

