### 11.2.1 Reporting of SAEs to Duke Cancer Institute Safety Desk

Adverse events that are serious and unexpected are considered reportable. Reportable events that occur during the study, beginning at the time of first study drug treatment infusion) to within 30 days following cessation of study drug treatment are reportable.

The study team will complete the DCI SAE Report Form and the DCI Safety Review Form, which will both be submitted to the DCI Safety Desk ([contact] or secure email to [[contact]](mailto:[contact])) and to the PI, [name], MD, FRCPC (email: [[contact]](mailto:[contact])) or her designee within 24 hours of knowledge of the event.

The initial report for each SAE should include at minimum the following information:

- protocol # and title
- patient initials, study identification number, sex, age or date of birth
- date the event occurred
- description of the SAE
- dose level and cycle number at the time the SAE occurred
- description of the patient's condition
- indication whether the patient remains on study
- causality or causal relationship

The DCI Safety Desk will track individual SAE reports into their internal tracking database and complete the initial processing within 2 business days of receipt. For unanticipated study-related event(s), these will be processed within 1 business day of receipt.

De-identified source documentation (i.e. admission notes, discharge notes, applicable laboratory results, radiology/diagnostic testing results, etc.) should be sent with the SAE Report Form, if available at the time of the report. Any follow-up information including severity, action taken, concomitant medications, and outcome should be communicated to the DCI Safety Desk, as soon as possible using the same forms mentioned above. The study team should keep a copy of the initial SAE forms submitted to the DCI safety desk and any SAE follow up forms for reference.

The DCI Safety Desk will use the information provided in the DCI SAE Report Form and the DCI Safety Review Form to complete a FDA Form 3500A, and will submit it to the Duke University IRB, if it meets Duke IRB reporting requirements (see below).

Only adverse events that the Duke Sponsor-Investigator determines to be serious, unanticipated, and related or possibly/probably (i.e. more likely than not) related to the research must be reported to the Duke IRB. Those adverse events will be submitted in the electronic IRB (eIRB) system, according the following guidelines:

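### AE recording ends at a mislabelled End of Treatment visit while safety follow-up runs to 30 days, so the key secondary safety proportion may miss late non-serious grade 3 or higher events

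*Combined protocol and SAP*

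**What the plan says.** Section 11.1 sets the recording rule, which starts at consent: "through the End of Study visit (as defined in Section 10.5), all AEs must be recorded". Entries go both in the chart and on the AE form. Section 10.5, to which it points, has a different title and content: "The End of Treatment visit, i.e. the date of a subject's last treatment visit, should include" a listed set of assessments. Section 10.7 is headed End of Study, but it says only when the trial as a whole is complete.

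Other sections use a later end point. Section 10.6 states: "Patients will be followed for safety a minimum of 30 days after last dose of study drug". Section 10.8.2 sets the same minimum for early withdrawals. Section 11.2.1 states: "Adverse events that are serious and unexpected are considered reportable", with a window from the first infusion to 30 days after treatment stops. Section 11.2.3 sends the study supporter any death within 30 days of the last dose, and all SAEs whether expedited or not.

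The key secondary analysis in Section 13.5.1 estimates, by cohort and dose level, "the proportion of patients who experience grade 3, 4, or 5 adverse events" at least possibly related to treatment. Neither that section nor the endpoint table in Section 6 states a time window or a data source.

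**The concern.** The section that governs the AE form stops earlier than the sections that govern safety follow-up, and it names a visit that its own cross-reference does not define. A site that follows 11.1 literally may stop entering AEs at the End of Treatment visit. A related grade 3 event that is not serious and begins after that visit then has no stated route into the database.

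This matters because grade 3 is the lowest grade that counts toward the key secondary endpoint, and an omission can only lower the proportion. Section 7.2 says the move to 24 mg/kg was made in the expectation that skin toxicity might become more frequent. It also reports that 16 of the first 19 patients at 18 mg/kg came off study for progression before 6 months. When treatment is short, the period after the last dose is a larger part of the time at risk.

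**Working it through.** The plan gives no expected rate or precision for this proportion, so there is no figure to reproduce. The check compares the sections and then sizes the gap under stated assumptions.

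**Step 1. End points side by side.**

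| Section | What it governs | Where it ends |
|---|---|---|
| 11.1 with 10.5 | AE case report form | End of Treatment visit |
| 10.6, 10.8.2 | Safety follow-up | At least 30 days after last dose |
| 11.2.1 | Serious, unexpected events | 30 days after stopping drug |
| 11.2.3 | Deaths, to the supporter | 30 days after last dose |
| 6, 13.5.1 | Key secondary proportion | Not stated |

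**Step 2. Which events are exposed.** Deaths to 30 days and SAEs reach the safety desk or the supporter through 11.2.1 and 11.2.3, and 10.6 follows new or unresolved related SAEs. What remains is mainly non-serious grade 3. No section says that events known only from SAE reports enter the analysis dataset.

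**Step 3. Length of the gap.** Let g be the days from the last infusion to the End of Treatment visit. The documents do not fix g, so it is an assumption. Uncovered days = 30 − g.

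- g = 0 (visit on the last infusion day): 30 days
- g = 14 (one dosing interval later): 16 days
- g = 28: 2 days

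The 14-day case fits a patient stopped at a scheduled scan. The last infusion is on Day 15 of a 4-week cycle, and the MRI precedes the next cycle about two weeks later (Section 10 schedule, Section 10.3).

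**Step 4. Gap as a share of follow-up time.** With k doses every 14 days, the window from first dose to 30 days after the last is 14(k − 1) + 30 days.

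- k = 4: window 14 × 3 + 30 = 72 days. Uncovered share 30/72 = 42%, 16/72 = 22% or 2/72 = 3% for g = 0, 14, 28.
- k = 8: window 14 × 7 + 30 = 128 days. Uncovered share 30/128 = 23%, 16/128 = 13% or 2/128 = 2%.

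These are shares of time. They equal shares of events only if the hazard is even, and the documents give no event timing.

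**Step 5. Effect on the proportion.** One patient whose only qualifying event is missed lowers the rate by 1/36 = 2.8 points in Cohort 1 or 1/29 = 3.4 points in Cohort 2 at full accrual. If a cohort stops after stage 1, the figures are 1/19 = 5.3 and 1/12 = 8.3 points.

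More generally, if p is the true proportion and q the share of affected patients whose only such event falls in the gap, the estimate drops by p × q. With assumed p of 20% to 40% and q of 5% to 30%, the drop runs from 0.20 × 0.05 = 1 point to 0.40 × 0.30 = 12 points. That is about 0.3 patients (29 × 0.01) to 4.3 patients (36 × 0.12) per cohort. The documents supply neither p nor q.

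**The case against.** The strongest reply is that this is a labelling slip with little consequence. Section 11.1 sets a minimum and forbids nothing later. Safety follow-up to 30 days is required, and 13.5.1 does not exclude events found then. The End of Treatment column in the Section 10 schedule carries MRI, laboratory tests and skin assessment but no infusion, so the visit probably falls after the last infusion. Section 10.8.2 points the same way, since it asks patients who withdraw early to complete the tests due at their next visit. The proportion is descriptive: sample size and error rates rest on PFS6, and the initial 24 mg/kg monitoring rule rests on events in the first cycle.

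Most of this stands. It makes the gap shorter than 30 days for many patients and makes the bias a possibility only. It does not remove the contradiction. The only definition that the AE rule points to is the End of Treatment visit, the schedule has no column after it, and nothing directs follow-up AEs onto the form.

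A reader might infer that a patient stopped at the first 8-week scan, after four infusions, has the whole last interval unrecorded, so that one in four events is lost. The schedule does not support this: the End of Treatment assessments for that patient would most likely be done at about week 8 and would cover that interval. A reader might also infer that expected toxicities are lost even when serious. Section 11.2.3 covers SAEs that are not expedited, so that is too broad.

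**Conclusion.** The end points in 11.1/10.5 and in 10.6, 10.8.2 and 11.2.1 are inconsistent, and 13.5.1 does not say which applies. As written, non-serious related events of grade 3 or higher after the End of Treatment visit need not be recorded. The key secondary proportion may therefore be biased low, at either dose level.

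The size cannot be fixed from the documents. It depends on when the End of Treatment visit falls and on how many patients have their only qualifying event after it. If few do, the effect is a fraction of a patient per cohort. It would be wrong to state that the proportion does miss toxicity after the final infusion: the follow-up is required, and serious events and deaths are known through safety reporting. No design figure changes. The point is worth correcting because the direction of any error is known and the remedy is small.

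**What to change.** In Section 11.1, correct the visit name and cross-reference, and require all AEs to be recorded through at least 30 days after the last dose of Sym004, matching Section 10.6. In Section 13.5.1, apply the same window to the key secondary proportion and to both AE tabulations, and state that events from SAE reports are included.

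The cost is a text change and a small amount of extra AE data at the 30-day follow-up. That follow-up is already required, but 10.6 names no visit or contact for it. The only contact interval given there is every 3 months, for progression and survival, so the plan should also say how the 30-day AE information will be obtained.
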